2.3 Potential Risks and Benefits

2.3.1 Potential Risks

The proposed research plan involves screening for clinical history, MRI safety, and global cognitive impairment; online surveys; neurological and movement examination, cognitive evaluation, performance-based tests, training via videoconferencing, pre-recorded psychoeducation lectures, and daily homework (listening to imagery audio files and filling out online surveys for the experimental group and taking brief online quizzes for the control group); and MRI scans. The potential risks associated with individual study procedures are as follows:

Immediate risks

Medication status

Subjects who are on medications for PD (e.g., carbidopa/levodopa, dopamine receptor agonists) will always be tested and scanned early in the day while they are on their regular medication regimen. This will minimize the risk of occurrence of symptoms related to being off medication such as excessive slowness or stiffness, freezing of gait, balance problems or falls, and severe anxiety.

Videoconferences for screening and training

The online Zoom platform will be used for videoconferences. There is no medical risk associated with videoconferences. There is a potential confidentiality risk (e.g., hacking of the conferences or user cameras).

Online surveys and homework

Online surveys and quizzes created on the Yale REDCap online database and survey platform will be emailed to subjects individually. Subjects will also submit their homework via REDCap. There is no medical risk associated with the online surveys and homework. No personally identifiable information will be collected, therefore, the surveys and homework do not pose a confidentiality risk.

Clinical, cognitive, and behavioral evaluation

The clinical evaluation including neurological and movement examination, paper-pencil tests for cognitive evaluation, and performance-based tests do not entail any medical risk. All of these evaluations will be performed in controlled laboratory settings. No personally identifiable information will be collected during these evaluations.

MRI in 3 Tesla scanner

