Capacity will be assessed directly in the course of attempting to obtain informed consent. When the member of the research team authorized to obtain consent has reviewed the study, they will ask the subject to explain the major elements of the study. Those elements are a) this is a research study (not routine treatment), b) participation is voluntary, c) study procedures, d) risks, e) benefits. Open-ended questions such as "Can you tell me the main things that you would do in this study? Can you tell me the main risks of the study?" will be used to assess understanding and appreciation of the facts. Subject will then be expected to

make a rational choice: "Considering the risks and benefits we have discussed, would you like to take part in this study?" Based on the subject's responses the team member will make a final judgment about capacity for consent. If the subject has capacity and agrees to the study, they will sign the consent form.

Subject monitoring

Subject's participation will be terminated under the following conditions: 1) Subject develops a serious medical condition. 2) Subject is not compliant with protocol evaluations. 3) Subject requests withdrawal from the study. Subjects may choose to stop participating in the clinical, cognitive, behavioral, and MRI evaluations at any time. During the experiments, the principal investigator or other members of the research team will be present at all times and monitor the subjects for adverse events. Subjects will maintain their regular medication regimen throughout the experiments. MRI scanning will be terminated immediately upon subject's request or if an adverse event occurs.

MRI-related risk management

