4.2 Outcome Variables

4.2.1 Primary Outcome Variables

1) Quality of life in Neurological Disorders (Neuro-QoL) Scores

Timeframe: This measure will be collected at baseline (T0), immediately after 6 weeks of intervention (T1), and 12 weeks thereafter (T2) from all subjects.

Rationale: The Neuro-QoL is a set of self-report measures that assesses the health-related quality of life of adults and children with neurological disorders. Neuro-QoL instruments were developed through a collaborative, multisite NINDS-sponsored research initiative to construct psychometrically-sound and clinically-relevant health-related quality of life measurement tools for individuals with neurological conditions including PD. The Neuro-QoL instruments enable within-disease as well as cross-disease comparisons and are intended for use in both neurology clinical trials and clinical practice. We will use the Neuro-QoL version 2 Cognitive Function item bank to assess post-training self-reported changes in cognitive functions.

Change in the Neuro-QoL version 2 Cognitive Function scores from T0 to T1 and across T2 will be the primary cognitive outcomes of this study. Significant increase in the Cognitive Function scores at T1 will be considered significant improvement in self-reported cognitive function in everyday life. Significant increase in these scores across T2 will be considered sustained improvement in self-reported cognitive function in everyday life.

2) Questionnaire on Mental Imagery (QMI) Vividness of Imagery Scale scores

Time frame: This measure will be collected at baseline (T0), immediately after 6 weeks of intervention (T1), and 12 weeks thereafter (T2) from all subjects.

Rationale: The QMI is a measure of vividness of an individual's multisensory and motor imagery on a scale of 1 to 7 (1: perfectly vivid image, 7: no image present at all).

Change in the QMI scores from T0 to T1 and across T2 will serve as the manipulation check for the mental imagery intervention. Significant increase in these scores at T1 will be considered improved imagery vividness. Significant increase in these scores across T2 will be considered sustained improvement in imagery vividness.

3) Task-specific whole-brain pairwise functional connectivity

Time frame: This measure will be collected at baseline (T0), immediately after 6 weeks of intervention (T1), and 12 weeks thereafter (T2) from all subjects.

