4.3.2 Eligibility Criteria/Vulnerable Populations

In order to be eligible for inclusion in the study, an individual must meet all of the following criteria:

- Subjects with a diagnosis of idiopathic PD defined according to the International Parkinson and Movement Disorder Society (MDS) Clinical Diagnostic Criteria for PD⁷⁵
- Age \geq 40 years
- Expected to be on a stable dopaminergic medication regimen throughout the study period

Any individual who meets any of the following criteria will be excluded from participation in this study:

- Age < 40 years
- Non-English speaking
- Pregnancy
- Breastfeeding
- Excessive alcohol consumption (> 7 drinks per week for women, > 14 drinks per week for men) or illicit substance use
- History of a neurological disorder such as a brain tumor, stroke, central nervous system infection, multiple sclerosis, movement disorder (other than PD), or seizures
- History of schizophrenia, bipolar disorder, attention deficit disorder, or obsessive-compulsive disorder
- History of head injury with loss of consciousness longer than a few minutes
- Metallic surgical implants or traumatically implanted metallic foreign bodies
- Inability to lie flat for about an hour in the MRI scanner
- Discomfort being in small, enclosed spaces
- Dementia at screening (Video-Montreal Cognitive Assessment score < 21/30⁸⁰⁻⁸²)
- Cognitive problems in activities of daily living suggestive of more than mild cognitive impairment (PD Cognitive Functional Rating Scale > 4⁸³)
- Mild cognitive impairment according to the MDS Level II comprehensive assessment criteria (> 2 SD below the norm in two tests in a single cognitive domain or in one test in two separate cognitive domains). Note: The cutoff of 2 SD below the norm will apply to all domains including attention, verbal and visual memory, language, visuospatial skills, and executive functions.⁷⁶
- Hoehn & Yahr stage > 3 (i.e., able to stand and walk, but not fully independent⁸⁴)
- Focal neurological findings on exam that suggest cerebral pathology other than that associated with parkinsonism
- Motor symptoms that could potentially introduce too much motion artifact in the imaging data (e.g., MDS-Unified PD Rating Scale resting tremor score > 2 in limbs, head/chin tremor, or more than mild dyskinesia by history or exam⁸⁵)
- Failure to adhere to training and homework requirements (i.e., less than 75% adherence to one-on-one sessions and less than 50% homework completion rate)

- Failure to adhere to protocol

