Online Homework and Quizzes: These will administered via the Yale REDCap online survey platform. Responses will be exported from REDCap.

- Quizzes on the psychoeducation material for the PD-Con group
- Surveys on the content of mental imagery homework for the PD-MI group

Clinical and Cognitive Evaluations:

- MDS-UPDRS and Hoehn & Yahr to assess disease severity (Visit 1)
- Wechsler Test of Adult Reading to determine premorbid IQ (Visit 1)
- RBANS test and executive function tests (Stroop, letter fluency (F-A-S), and Trail Making Test parts A and B) for a comprehensive cognitive evaluation (Visits 1, 3, and 4)
- Neuro-QoL survey (primary cognitive outcome) to assess the impact of cognitive functioning on activities of daily living (Visits 1, 3, and 4)
- Structured cognitive interview for the PD-MI group to determine subjects' cognitive difficulties during everyday tasks (Visit 1)
- QMI Vividness of Imagery Scale will serve as a manipulation check for the mental imagery intervention (Visits 2, 3, and 4)

- Modified Six-Elements Test as a performance-based measure of goal-directed planning and execution (Visits 1, 3, and 4)

Case report forms for each subject will be used to enter clinical evaluation results, and scores of paper-pencil tests, online surveys, and performance-based tests. All of this information will then be entered into a password-protected electronic database, which will be stored in a group-owned ([name] Lab) shared space on a Yale REDCap database.

Imaging Data:

Functional MRI data during mental imagery and video-watching tasks will be collected in a 3 Tesla human magnet at the MRRC (Visits 2, 3, and 4). The fMRI data will be used for functional connectivity analyses to evaluate the changes in whole-brain functional connectivity (primary imaging outcome) and other network measures as a result of the mental imagery intervention.

Imaging data will be transferred securely to workstations for analysis and stored on HIPAA-compliant secure central storage servers ("Storage@Yale") provided by the Yale IT Department for a monthly fee.

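### Randomised subjects who are terminated under section 2.3.1 or excluded for non-adherence under section 4.3.2 have no planned Neuro-QoL follow-up, so some primary data may be lost avoidably; the likely bias is small and the remedy cheap.

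*Combined protocol and SAP*

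**What the plan says.** Two rules end the participation of randomised subjects.

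- **Section 2.3.1, in the part on minimising risk, states:** "Subject's participation will be terminated under the following conditions: 1) Subject develops a serious medical condition. 2) Subject is not compliant with protocol evaluations". A third condition is the subject's own request.
- **Section 4.3.2:** "Any individual who meets any of the following criteria will be excluded from participation in this study". The list that follows includes falling short on training and homework, defined as under 75% of one-on-one sessions and under 50% of homework completed, and, as a separate item, "Failure to adhere to protocol". Section 4.1.1 places randomisation at the end of Visit 1, before any training, so training and homework adherence can only be judged in people already randomised.

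On the outcome, section 4.2.1 says of Neuro-QoL: "This measure will be collected at baseline (T0), immediately after 6 weeks of intervention (T1), and 12 weeks thereafter (T2) from all subjects". Section 5.1.1 ties it to three in-person visits: "Neuro-QoL survey (primary cognitive outcome) to assess the impact of cognitive functioning on activities of daily living (Visits 1, 3, and 4". No section provides for Neuro-QoL after termination or exclusion, and none distinguishes stopping training from leaving follow-up. The nearest text lets one component stop alone: "MRI scanning will be terminated immediately upon subject's request or if an adverse event occurs".

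Section 5.4.6 assumes data are missing at random. It uses complete cases if no more than 5% are missing, and multiple imputation of the primary cognitive outcome otherwise.

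**The concern.** Someone who falls seriously ill, misses a scan or adheres poorly may still be able and willing to answer a questionnaire. Once participation has ended, the plan gives staff no basis for asking. The loss is then created by the study, not by the subject, and in part it follows ill health, which may plausibly affect self-reported cognition.

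The analysis would fill the gap with values imputed under missing at random, an assumption the data cannot check. Bias in the comparison needs two things. The lost subjects' true change must differ from what is imputed, and either the number lost or the size of that departure must differ between arms.

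Equal loss is not guaranteed. One-on-one sessions exist only in PD-MI (section 5.1), so the 75% threshold, read literally, has no counterpart in PD-Con. The general item on protocol adherence could reach either arm.

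**Working it through.** **1. The plan's own figures (section 5.4.2).** Inputs: f = 0.266, alpha 0.05, two groups, two measurements. The correlation is not stated; 0.5 is assumed.

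- Noncentrality = f² × N × m / (1 + (m − 1)ρ) = 0.266² × 86 × 2 / 1.5 = 8.11. Power is 0.804, so the stated 86 is reproduced.
- Dropout: 86/0.85 = 101.2 and 101/0.85 = 118.8, in line with the stated 101 and 120.

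The point below alleges no error in these figures.

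**2. How many subjects could be involved.**

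- Planned loss by T1: 0.15 × 120 = 18. By T2: 120 × (1 − 0.85²) = about 33.
- Section 5.3.2 says the earlier imagery study's 15% counted homework non-compliers together with non-completers, and expects no more than 15% here. Excluded non-adherers are therefore part of the budgeted 18, not an addition to it. The documents do not give the split.
- Imputation trigger: more than 0.05 × 120 = 6 missing. If 25%, 50% or 75% of the 18 could be recovered, 13.5 (11.3%), 9 (7.5%) or 4.5 (3.8%) would remain missing. At least 12 of the 18 must be recovered to reach 5% or less.

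**3. Size of a possible shift.** Let k be the subjects lost in an arm and d the amount by which their true change falls short of the imputed change.

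Shift in arm difference = (k_MI × d_MI − k_Con × d_Con) / 60

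The values of k and d are assumptions. The range 2 to 6 for d borrows the span that section 5.4.2 gives for a minimally important change.

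| Assumed case | Shift (T-score) |
|---|---|
| 3 excess in one arm, d = 2 | 3 × 2/60 = 0.10 |
| 3 excess in one arm, d = 4 | 3 × 4/60 = 0.20 |
| 3 excess in one arm, d = 6 | 3 × 6/60 = 0.30 |
| 3 lost per arm, same d | 0 |
| 3 lost per arm, d = 6 and 2 | 3 × (6 − 2)/60 = 0.20 |

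If half could still answer, the fix removes half of the one-arm shift: 0.05 to 0.15. A shift of 1 T-score needs 60/6 = 10 to 60/2 = 30 excess losses in one arm.

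A simulation with 60 per arm, SD 7.25, correlation 0.7 and regression imputation from baseline within arm (8,000 runs) agrees. Three excess losses at d = 2 and d = 6 gave 0.098 and 0.299. Three per arm at d = 6 and 2 gave 0.201, and three per arm at d = 4 in both gave −0.001.

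**4. Against the standard error.** With the planned 15% loss, 51 per arm have data. SD 7.25 is from section 5.4.2; the baseline to follow-up correlation r is assumed.

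SE = 7.25 × √(2(1 − r)) × √(2/51) = 1.44 at r = 0.5, or 1.11 at r = 0.7

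The range is 0.10/1.44 = 0.07 to 0.30/1.11 = 0.27 of a standard error.

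**The case against.** The case against giving this much weight is good, and most of it stands.

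- **The plan is silent; it does not forbid follow-up.** Sections 4.1.1 and 5.1 have all subjects returning for Visits 3 and 4, and section 2.3.1 lets subjects stop individual evaluations. That is fair, but these are general statements. They do not reach a person whose participation the same document has ended.
- **The recoverable group is small.** As worded, the adherence rule joins its two thresholds with an and: a subject must fall below both. Such people are largely disengaged and may not answer a later survey. Neuro-QoL is itself one of the evaluations, so someone who skips Visits 3 and 4 entirely would often lack it anyway. Those who withdraw on request are outside the point. Treating one missed scan as non-compliance that ends everything is an inference.
- **Loss is already budgeted, and imputation is planned.** True. The issue is therefore possible bias more than power.
- **A 6-point shortfall is generous.** Losing the whole planned benefit is 4 points, which gives 0.20 for three subjects.
- **Remote scores confound mode with illness or non-adherence.** This is a real but limited cost.

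A reader might infer that these losses come on top of the 15%, or that the imputation trigger would be passed with or without these rules. Section 5.3.2 does not support the first. The second depends on how many of the 18 are recoverable. A reader might also infer that PD-MI will lose more subjects. The wording permits that, but the only between-arm evidence, from the earlier imagery study, showed no significant difference in dropout.

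**Conclusion.** The gap is real: two clauses end participation in randomised subjects, and nothing preserves their primary outcome. It is more than missing detail, because following the plan as written discards scores that some subjects could still give.

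Its consequence is probably small. The illustrated shift of 0.10 to 0.30 T-score rests on an assumed excess of three losses in one arm and an assumed shortfall of 2 to 6. It vanishes when losses and departures match between arms. The documents do not give the number affected; the planned 18 of 120 by T1 is the only ceiling they offer, and it is a planning allowance.

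It would be tempting to conclude that the primary comparison is threatened. The documents do not support that: a shift of even 1 T-score against the planned 4 would need 10 to 30 excess losses in one arm. This is a worthwhile, inexpensive improvement, held with medium confidence.

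**What to change.** In sections 2.3.1 and 4.3.2:

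1. Separate stopping training, scanning or in-person testing from withdrawing from follow-up.
2. Ask every randomised subject for Neuro-QoL at the nominal T1 (6 weeks after training starts) and T2 (12 weeks later), by REDCap or Zoom if needed, unless the subject withdraws consent to follow-up.
3. Analyse these scores in the randomised arm.
4. Record which component was stopped and why, and flag remotely collected scores.

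Medical stopping of training or scanning is unchanged, and so is the required sample size. Feasibility is not in doubt: surveys already run through REDCap, and section 2.3.1 says of the clinical and cognitive assessments: "The clinical evaluation including neurological and movement examination, paper-pencil tests for cognitive evaluation, and performance-based tests do not entail any medical risk".

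The cost is protocol and consent wording plus a few remote surveys. The downside is a small number of scores collected in a different mode, mostly from ill or non-adherent subjects. The flag allows a check with those scores left out.

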2.3.2 Potential Benefits

Immediate potential benefits

Subjects with PD in the experimental group will most likely experience a direct benefit from the mental imagery intervention in terms of improvement in cognitive functioning in everyday life. Similarly, subjects with PD in the active control group will most likely experience a direct benefit from psychoeducation in terms of gathering information about cognitive problems experienced in PD and management and coping strategies.

Long-Range Potential benefits

The knowledge gained from this study will facilitate the design and implementation of a phase 2 clinical trial. Ultimately, it is highly likely that mental imagery training will be incorporated into cognitive rehabilitation programs and will lead to improvements in the treatment of cognitive problems of individuals with PD.

3 Study Purpose and Objectives

3.1 Hypotheses

We hypothesize that our 6-week mental imagery training protocol will improve goal-directed cognitive functioning in everyday life of PD patients. Furthermore, we predict the effects of mental imagery will increase task-specific whole-brain functional connectivity and improved differentiation of core brain networks. We hypothesize that the training effects on A)

goal-directed cognitive functioning and B) functional network re-organization will be sustained over the course of 12 weeks post-intervention in the PD-MI group, but not in the PD-Con group.

Lastly, we hypothesize that the putative task-specific within- and between-network functional connectivity changes in the PD-MI group at the 6- and 12- week timepoints will predict the corresponding self-reported, performance-based, and executive function test outcomes.

3.2 Primary Objective

The primary objective of this study is to determine whether mental imagery training will improve goal-directed cognitive functioning in everyday life and brain functional connectivity in patients with PD.

3.3 Secondary Objective

The secondary objective is to determine whether the behavioral and imaging effects (as outlined in the primary objective) of mental imagery training are sustained after a 12-week period in patients with PD. A final exploratory objective is to determine if there is a potential brain-cognition link to predict the corresponding cognitive functional outcomes.

4 Study Design

4.1.1 General Design Description

We will conduct a phase 1 clinical trial with two groups randomly assigned in parallel. The experimental group (PD-MI) will receive mental imagery training and the control group (PD-Con) will receive psychoeducation (see Figure 3).

Within two weeks of obtaining consent and completing initial phone and online video-screening, subjects will complete online surveys and arrive for an in-person visit to complete the screening process including the comprehensive evaluation of baseline cognitive functioning, performance-based tests, and neurological exam. At the end of this visit, eligible subjects will be randomized to two groups, PD-MI and PD-Con.

Within two weeks of Visit 1, subjects will return for Visit 2 to assess baseline imagery skills and perform fMRI tasks in the scanner. Subjects in the PD-MI group will be interviewed in Visit 2 to gather information about their daily activities and goals for imagery script development.

Following Visit 2, subjects will start their respective trainings for 6 weeks. The one-on-one training sessions will be delivered via videoconferencing.

We will guide the subjects in the PD-MI group using personalized scripts during one-on-one mental imagery training 3 times a week for the first 4 weeks. We will also record the mental imagery scripts (each 5-10 min) for self-practice on none-training days in the first 4 weeks and for daily homework in the subsequent 2-week block. After each daily practice in the 2-week block, subjects will be asked to submit a detailed mental imagery diary via the Yale REDCap online survey platform. Subjects will also be called once a week in the 2-week block for check-in.

[figure not shown]
The control group (PD-Con) will receive psychoeducation 3 times a week for 4 weeks regarding cognitive functioning and brain health in PD. Subjects will receive private video links with pre-recorded PowerPoint lectures covering topics such as basic brain anatomy, neuroplasticity, attention-executive function, memory, speech-communication, hallucinations and delusions, sleep, diet, physical activity, mood disorders, stress, and social bonds. On no-lecture days and in the subsequent 2-week block, subjects will receive online quizzes covering the lecture topics to be completed via Yale REDCap online survey platform. Subjects will also be called once a week in the 2-week block for check-in.

Upon completion of the 6-week training, all subjects will return for Visit 3 which will entail repeat cognitive evaluations and performance-based tests as in Visit 1, and mental imagery vividness rating and fMRI scans as in Visit 2. After Visit 3, subjects in the PD-MI group will be

encouraged to incorporate goal-directed mental imagery into their daily life and those in the PD-Con group will be encouraged to retain the psychoeducation material they learnt.

Twelve weeks after Visit 3, all subjects will return for Visit 4 which will be the final visit and entail repeat evaluations of all cognitive and performance-based tasks and the fMRI tasks. The same procedures as described in Visit 3 will be followed.

Figure 3. Study Flow

